The utility of smartphone applications for patient care is increasingly being appreciated and in Europe, clear guidelines exist for developers who aim to develop software as a medical device (6). The advantage of using smartphone applications is that little specialised equipment is needed and, if a digital support programme is proven successful, implementation can be widely performed at low cost.

In the current context of the Covid-19 pandemic, HF patients are particularly suffering from the difficulty to meet their cardiologist and HF nurse on a regular basis. Developing the possibility for remote monitoring is a key alternative to avoid re-hospitalization or severe clinical cardiovascular outcome.

We present the design of the Bedicare-HF trial, which aims to take digital support research a step further. It uses an implementation design approach in which a real-life setting will be approximated. The trial aims thus to not only demonstrate the effectiveness of a smartphone-based HF digital support approach but also the feasibility of implementation in a European healthcare context. Also, it aims to evaluate the cost-effectiveness of a smartphone-based digital support approach.

Objectives

The objectives of this study are to demonstrate feasibility, acceptability, adoption, sustainability, and safety of a smartphone-based digital support system in the healthcare system in Belgium and to demonstrate effectiveness, to evaluate the implementation cost of the system, and to demonstrate cost-effectiveness.

Methods

Study design

The study design is a multicentre implementation trial. The conduct of the study is guided by good clinical practice (GCP) in accordance with the Declaration of Helsinki and the laws and regulations applicable in Belgium. Written approval from the Ethics Committees at all involved centres is required and informed consent must be provided by each patient.

Patient recruitment

Eligible patients are consecutive patients that are hospitalised for HF decompensation. The patients will be included in the programme during their hospitalisation or up to one week after hospitalisation. All eligible patients will be offered to participate. At the time of inclusion,

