patients must be in New York Heart Association (NYHA) class II, III, or IV with a left ventricular ejection fraction (LVEF) of ≤40%. The inclusion and exclusion criteria are shown in Table 1. A total of 165 patients will be included over 6 month. In total, 11 hospitals (local investigators) in Belgium with an HF clinic employing at least one certified HF nurse will be participating in patient recruitment. Patients are not randomised and will all be participating in the smartphone digital support intervention.

A screening register will be kept including reasons why eligible patients that do not participate are disregarding inclusion. Patients refusing participation will also be asked to complete a quality of life (QOL)-questionnaire at 6 months and 12 months which will be answered online. A total of 165 patients (who do not want to participate) will be asked to answer this questionnaire.

So the app will be made available to 165 patients for home monitoring and another group of 165 patients without an application will be asked to answer quality of life questionnaires.

Patients who agree to use the application can continue to use it after the study, if they wish.

Inclusion criteria	Exclusion criteria
Diagnosed with HF – NYHA class II-IV	Acute coronary syndrome
LVEF ≤40%.	High urgent listed for heart transplantation
Hospitalisation due to decompensated HF at the moment of inclusion or up to 1 week prior to inclusion (i.e. discharged ≤1 week prior to inclusion).	Planned revascularisation, TAVI, MitraClip and/or CRT implantation within 3 months after inclusion
Owning a smartphone and able to use an application	Known alcohol or drug abuse
Written informed consent obtained	Terminal renal insufficiency with haemodialysis or peritoneal dialysis
	Impairment or unwillingness to use the digital support equipment (e.g. dementia, impaired self-determination, lacking ability to communicate)
	Existence of any non-cardiac disease reducing life expectancy to less than 1 year
	Age <18 years
	Participation in other treatment studies or remote patient management programmes

Table 1 – Inclusion and exclusion criteria. NYHA: New York Heart Association. LVEF: left ventricular ejection fraction. CRT: cardiac resynchronisation therapy. TAVI: transcatheter aortic valve implantation.

Digital support platform

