Comunicare Solutions SA will provide patients with a **GDPR policy**, as required to inform the patient about his/her rights related to their personal data. The hospital will provide the patients with an informed consent document.

Data processing: clinical study

Comunicare Solutions SA will provide each participating centre an appropriate number of patient access cards. Each patient access card displays an anonymous user ID and password as well as a scannable QR code. Once the written informed consent form (ICF) is obtained, the study personnel at each participating centre will add the patient to a ICF log (spreadsheet) and attribute a study number to each participant. The hospital study personnel will assign a specific patient access card to the participant and register its code on the ICF log. Data entered into the App and transferred to the sponsor's database will thus be fully anonymized.

The ICF log will allow the hospital study personnel to reconcile data with individual patient identity and should be kept by hospital study personnel in a secured location. Therefore, only the medical staff under the responsibility of the investigator in each participating centre will be able to establish a link between the identity of the patient and the data collected throughout the study. The ICF log will not be communicated to the sponsor.

For the statistical analysis, the scientific staff of the Heart Centre Hasselt will only receive and process anonymized data. The generation of anonymous patient code is done via a Universally Unique Identifier (UUID), a 128-bit label generated according to standard methods (<https://www.ietf.org/rfc/rfc4122.txt>) that guarantee the uniqueness and the non-reversibility. Therefore, the Heart Centre Hasselt will not process any personal data and is therefore not subject to GDPR requirements.

Intervention design

The assessments performed at each visit are displayed in Table 2. At inclusion, laboratory values and echocardiography results of ≤ 2 weeks prior to inclusion performed as part of routine care will be used.

Smartphone intervention

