Table 2 – intervention design. ECG: electrocardiogram. ePRO: electronic patient-reported outcome. NT-proBNP: N-terminal prohormone of brain natriuretic peptide. KCCQ-12: Kansas City Cardiomyopathy Questionnaire. EQ5D: EuroQol 5-dimension questionnaire. HeartQoL: Health-related quality of life questionnaire. PHQ9: patient health questionnaire-9. HLS-EU-Q16: European Health Literacy Survey Questionnaire. EHFSB-9: European Heart Failure Self-care Behaviour scale revised into a nine-item scale. SUTAQ: Service User Technology Acceptability Questionnaire. WPAI : work productivity and impairment.

Health economic analysis

The costs considered for the cost-effectiveness analysis are direct costs of the smartphone-based digital support intervention and the care utilisation recorded during the inclusion of the trial. The costs for the digital support intervention consist of costs for data management using the application, costs for devices that are provided in selected patients (blood pressure monitor, weighing scale), and personnel costs for inclusion and time spent on follow-up of alarms.

Information on care utilisation will be collected at the end of the trial. Former studies have demonstrated that hospitalisation costs are the key driver of HF-related costs (7,8). This study will thus focus on reduction in length of hospital stay and reduction in rehospitalisations after initial hospitalisation. The 30-day and 90-day rehospitalisation rates will be assessed. All hospital-related costs will be collected from the hospital billing and financial departments. A distinction will be made between scheduled and non-scheduled hospitalisations. Scheduled hospitalisations for elective procedures and scheduled visits with the cardiologist or general practitioner will not be included in the cost-evaluation.

Implementation cost and cost-effectiveness will be assessed in this trial following a pre-post economic model. A historical cohort of all patients hospitalised for HF on a cardiology ward in 2019 in all participating centres will be assessed for comparison. Hospital bills and hospital administrative data based on the international classification of disease (ICD)-codes will be collected. Propensity matching will be applied.

QOL and healthcare-related costs will be collected in selected patients refusing to participate in the smartphone intervention.

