Cost reduction between the intervention group, the historical cohort, and the participation refusals will be calculated. Costs and outcomes (utilities) will be compared by calculation of the incremental cost-effectiveness ratio (ICER) (ICER = $(\text{cost}_{\text{intervention group}} - \text{cost}_{\text{historical cohort}}) / (\text{effectiveness}_{\text{intervention group}} - \text{effectiveness}_{\text{historical cohort}})$). The incremental cost represents the difference in total average cost per patient between the intervention group and the historical cohort or the participation refusals. Effectiveness will be calculated by comparing QOL in the intervention group versus the participation refusals.

Study endpoints

The endpoints that will be assessed are summarized in Table 3. As specified before, the objectives of the study are to demonstrate positive implementation measures (e.g. feasibility) as well as to demonstrate cost-effectiveness. Secondary objectives include assessment of clinical impact, based on measurement of clinical endpoints as specified in Table 3. Implementation outcome variables will be assessed using a mixed-method design. Patient and caregiver parameters will be calculated (e.g. time spent using the application). Questionnaires will be used to assess patient variables. Semi-structured interviews in a selection of patients and caregivers will be performed to assess further outcome variables regarding implementation.

Implementation outcome variables	
Feasibility and patient acceptability	SUTAQ, semi-structured interviews.
Caregiver acceptability and burden of care	SUTAQ, semi-structured interviews, daily time spent by case nurses using the platform
Adoption and sustainability	Number and percentage of patients refusing inclusion, of patients continuing application usage after 6 months. Total time-percentage ratio of patients using the application throughout the trial.
Implementation cost	Cost-related data: healthcare resource use, hospital days, tests, procedures, health expenditure. Cost-effectiveness: healthcare cost data, WPAI questionnaire, ICER. Cost of hospital stay at inclusion.
Quality of life, literacy and patient self-care	KCCQ-12, EQ5D, HeartQoL, PHQ9, HLS-EU-Q16, EHFSB-9, SUTAQ.
Clinical outcome measurement	
Combined endpoint	Unplanned CV readmission and all-cause mortality

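### The 2019 cost comparator is drawn from all heart-failure admissions without the trial's LVEF ≤40% and Table 1 criteria, and matching on bills and ICD codes cannot be relied on to remove the difference

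*Protocol*

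**What the plan says.** The protocol's Patient recruitment section and Table 1 admit patients in NYHA class II–IV "with a left ventricular ejection fraction (LVEF) of ≤40"%. They must also meet the condition "Owning a smartphone and able to use an application". Table 1 excludes, among others, acute coronary syndrome, dialysis, certain planned cardiac procedures and non-cardiac disease limiting life to under one year. On timing: "The patients will be included in the programme during their hospitalisation or up to one week after hospitalisation".

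The Health economic analysis section sets up a pre-post model. Its comparator is described as follows: "A historical cohort of all patients hospitalised for HF on a cardiology ward in 2019 in all participating centres will be assessed for comparison". The next two sentences give the data and the adjustment: "Hospital bills and hospital administrative data based on the international classification of disease (ICD)-codes will be collected. Propensity matching will be applied". On outcomes it states: "This study will thus focus on reduction in length of hospital stay and reduction in rehospitalisations after initial hospitalisation".

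The printed ICER formula subtracts the historical cohort's cost in the numerator. The accompanying text adds: "The incremental cost represents the difference in total average cost per patient between the intervention group and the historical cohort or the participation refusals". The refusal group comes from eligible patients who decline (Patient recruitment), and costs are collected for a selection of them.

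**The concern.** The two sides of the historical contrast are defined differently. One side is restricted to reduced ejection fraction and a list of exclusions. The other is every heart-failure admission to a cardiology ward in one year. Matching can narrow the gap only through variables that are recorded, and the sources named for 2019 do not include the main one, LVEF.

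Demonstrating cost-effectiveness is a stated objective, hospital stay and rehospitalisation are the declared focus of the economic analysis, and the Discussion expects a successful result to bear directly on reimbursement. If cost or readmission varies with LVEF among patients with the same coded profile, part of the historical cost difference would be case mix rather than an effect of the application. A larger matched sample would not reduce that part.

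**Working it through.** **Side by side (Protocol)**

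| Item | Participants | 2019 pool |
|---|---|---|
| LVEF | ≤40% required; routine echo used | No limit stated; not among the named data |
| NYHA | II–IV | No limit stated; not among the named data |
| Acute coronary syndrome, dialysis | Excluded | Not excluded, but probably visible in codes or bills |
| Smartphone ability, willingness | Required | Not among the named data |
| Calendar period | During Covid-19 | 2019 |

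The protocol states no figure for this contrast, so there is nothing to reproduce. The calculations below are illustrations; except for the 165 participants, every input is an assumption.

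**1. Shift in mean cost.** Let f be the share of matched 2019 patients with LVEF >40%, and g the fractional difference in their mean cost from that of patients with LVEF ≤40%. The comparator mean shifts by f × g.
- f = 0.2, g = 10%: 0.2 × 10% = 2%.
- f = 0.6, g = 30%: 0.6 × 30% = 18%.
- g = 0: no shift.

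The sign follows the sign of g, which the protocol does not give.

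**2. How much matching on coded data might remove.** Let p be the share of the pool with LVEF >40%. Let a coded score X follow N(0,1) if LVEF >40% and N(d,1) if LVEF ≤40%, with d = √2 × Φ⁻¹(AUC). After exact matching on X, the residual share with LVEF >40% is

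r = E over X ~ N(d,1) of pφ(X) / [pφ(X) + (1−p)φ(X−d)].

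With RR the readmission risk at LVEF >40% relative to ≤40% at the same X, the apparent participant/historical ratio with no effect of the application is 1/[1 + r(RR−1)].

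| Matching | p | r | RR 0.8 | RR 1.3 |
|---|---|---|---|---|
| None | 0.2 | 0.200 | +4.2% | −5.7% |
| None | 0.6 | 0.600 | +13.6% | −15.3% |
| AUC 0.7 (d = 0.742) | 0.2 | 0.183 | +3.8% | −5.2% |
| AUC 0.7 | 0.4 | 0.353 | +7.6% | −9.6% |
| AUC 0.7 | 0.6 | 0.529 | +11.8% | −13.7% |
| AUC 0.9 (d = 1.812) | 0.2 | 0.115 | +2.3% | −3.3% |
| AUC 0.9 | 0.4 | 0.207 | +4.3% | −5.8% |
| AUC 0.9 | 0.6 | 0.310 | +6.6% | −8.5% |

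A plus sign means that participants look worse, a minus sign that they look better. Under this model weakly informative codes remove little of the imbalance, and strongly informative codes remove about half or somewhat less.

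**3. In counts.** Take 165 per group, 20% readmission risk, p = 0.4 and AUC 0.7. Participants: 165 × 0.20 = 33.0. Matched controls: 33.0 × (1 + 0.353 × (RR−1)) = 30.7 at RR 0.8 and 36.5 at RR 1.3. The shift is −2.3 to +3.5 readmissions. Under the same assumptions the standard deviation of the difference between two independent groups is √(2 × 165 × 0.2 × 0.8) = 7.3.

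**The case against.** **The matched subset is the real comparator, and an analysis plan that is not shown may filter the pool.** Matching covariates, calipers and balance checks can indeed be left to that plan, and naming two sources does not rule out others. A reader might infer that matching cannot balance LVEF; the document does not support that. It does fix the pool and the data to be collected, and an LVEF filter needs data that the protocol does not list.

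**The refusal group already supplies an eligible cost contrast.** This stands. By the protocol's wording refusers are eligible patients, so their contrast does not carry the LVEF mismatch, although they are self-selected. It does not repair the historical contrast, which is the one in the printed formula.

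**The magnitude is soft.** This also stands. The detailed figures concern readmissions rather than cost, rest on assumed inputs and fall on both sides of zero. In the worked case the shift is under half of one standard deviation of sampling noise. A reader might infer that the comparison is tilted in favour of the application; nothing in the protocol gives a direction.

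**NYHA adds little.** Agreed: the criterion removes only class I, which should be few among patients hospitalised for heart failure.

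**The limitation is disclosed.** The Discussion admits that there is no distinct comparator and that a historical cohort is needed. It does not mention that this cohort is defined more broadly than the trial population.

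**Conclusion.** The point holds for the historical ICER cost contrast only. The 2019 pool is defined without the trial's LVEF and Table 1 criteria, and the named data give no assurance that matching restores comparability on LVEF. Size and direction are unknown. The illustrative 2–18% shift in mean cost depends wholly on assumed shares and cost differences, and the LVEF component is zero if cost does not vary with LVEF.

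A reader might infer that the study's main results are compromised. They are not touched by this: the paired baseline, 6-month and 12-month tests do not use the 2019 cohort, and neither does the refusal-group cost contrast. This is an inexpensive improvement to make before the 2019 data are extracted.

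**What to change.** - **Filter before matching.** Restrict the 2019 pool to patients who meet the Table 1 criteria readable at the index stay: adult, no acute coronary syndrome, no dialysis, and LVEF ≤40% from existing echo reports, looked up only for those who pass the administrative filters. Do not infer planned procedures from procedures performed later, because that selects on follow-up.
- **Report the gaps.** Give the number of 2019 patients with no readable LVEF. If a centre cannot do the look-up, use the coded filters there and state the residual LVEF imbalance.
- **Align time zero.** Count 30- and 90-day rehospitalisation from index discharge in both groups, and apply any restriction to patients discharged alive to both groups. For participants included after discharge, require the matched 2019 patient to be alive and free of heart-failure readmission at the same delay: a participant readmitted in that week could qualify through the new stay, so late inclusion generally implies no such readmission. Add a sensitivity analysis limited to participants included in hospital.
- **Show the refusal-group cost contrast alongside**, and state that smartphone ability, willingness to take part and calendar period (2019 versus Covid-19) remain unbalanced.

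**Cost.** A smaller comparator cohort, a limited record review at 11 hospitals, and an amendment that the Ethics Committees must approve before it is implemented. For participants the protocol already relies on routine imaging ("echocardiography results of ≤ 2 weeks prior to inclusion performed as part of routine care will be used"), so reports probably exist for many 2019 patients, but their completeness is unknown.

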Interventions because of the trial

Personalised alarm cut-offs can be programmed by the caregiver team. There is no scheduled study contact on top of the usual care contacts. In case of application alarms being triggered, the patient will be called and the situation will be assessed. If needed, the problem will be discussed with a cardiologist. In emergency situations, the patient will be asked to present to the emergency department.

Monitoring of alarms will not be continuous and will only take place during working hours throughout the working week (Monday to Friday) and patients will be instructed to call their general practitioner, the hospital, or the emergency number in case of problems and not to wait until they are contacted.

End-of-trial assessment

At the end of the trial, the assessments listed in Table 2 will be performed. Cost-related data will be collected: healthcare resource use, hospitalisation time, tests, procedures, and health expenditure. Cost-effectiveness will be calculated using healthcare cost data and work productivity and impairment (WPAI) questionnaire to calculate incremental cost-effectiveness ratio (ICER).

Re-evaluation at 12 months

After the end of the inclusion at 6 months, a re-evaluation of outcome parameters will take place at month 12 to evaluate the continued effect of the intervention after cessation.

	Baseline	Final visit month 6
Informed consent and patient information	X	
Medical history: past medical history, symptom control, NYHA classification, smoking behaviour, current medication	X	X
Physical examination including weight, height, blood pressure, heart rate	X	X
Length of initial hospital stay	X	
Registration of medication	X	X
Echocardiography	X	X
12-lead ECG	X	X
Laboratory tests: haemoglobin, haematocrit, leukocytes, thrombocytes, sodium, potassium, creatinine, NT-proBNP	X	X
ePROs: KCCQ-12, EQ5D, HeartQoL, PHQ9, HLS-EU-Q16, EHFSB-9, SUTAQ, WPAI.	X	X
Registration of events: hospitalisation (with the length of stay), emergency department visit, death		X
Cost-evaluation		X

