Individual endpoints	Symptom control (NYHA, KCCQ-12), emergency department visits, length of hospital stay during the trial, unplanned CV readmission, all-cause mortality.

Table 3 - Study endpoints. CV: cardiovascular. SUTAQ: Service User Technology Acceptability Questionnaire. KCCQ-12: Kansas City Cardiomyopathy Questionnaire. EQ5D: EuroQol 5-dimension questionnaire. HeartQoL: Health-related quality of life questionnaire. PHQ9: patient health questionnaire-9. HLS-EU-Q16: European Health Literacy Survey Questionnaire. EHFSB-9: European Heart Failure Self-care Behaviour scale revised into a nine-item scale. SUTAQ: Service User Technology Acceptability Questionnaire. WPAI : work productivity and impairment. ICER: incremental cost-effectiveness ratio.

Statistical analysis

Sample size

A total of 165 patients will be included in the study. The sample size is based on comparable implementation trials (9,10). An additional patient group will be included that is not part of the study intervention but will complete questionnaires; this is a non-randomized control group. A minimum of 165 patients will take part in this control group for completion of the study.

Statistical analysis

The primary analyses will be paired Student *t*-tests and Wilcoxon signed-rank tests comparing baseline, 6-month and 12-month values for all patient-level outcomes. Secondary analyses aimed at determining the longitudinal impact of the smartphone digital support programme (i.e., using outcome data from the additional time points), and the correlation of independent variables (e.g., patient characteristics and adherence rates) with outcomes will be analysed using general linear mixed-model procedures. In addition, descriptive statistics will be produced for all variables collected, and subgroup analyses will be performed. All statistical analyses will be performed using the statistical software application SPSS (IBM Corporation, USA).

Descriptive statistics will be produced for the indicators of the implementation outcome to provide an objective measure of implementation success.

Discussion

The Bedicare-HF study is the first study that will investigate implementation of a smartphone-based HF digital support system in a real-life context on the background of European GDPR and medical device regulations.

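### Refusers serve as comparator for quality of life and costs, but no registration of their deaths, readmissions or emergency visits is planned, so a death cannot be told from non-response

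*Protocol*

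**What the plan says.** **App group.** The assessment table is captioned "Table 2 – intervention design". Its month-6 column contains the row "Registration of events: hospitalisation (with the length of stay), emergency department visit, death". Table 2 has no row or column for refusers.

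**Refusers.** Three places describe what they contribute:
- Patient recruitment: "Patients refusing participation will also be asked to complete a quality of life (QOL)-questionnaire at 6 months and 12 months", and again that "another group of 165 patients without an application will be asked to answer quality of life questionnaires".
- Health economic analysis: "QOL and healthcare-related costs will be collected in selected patients refusing to participate in the smartphone intervention".
- Sample size: an additional group of at least 165 that fills in questionnaires, of which the text says "this is a non-randomized control group".

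**How refusers are used.** The Health economic analysis section compares costs between the app group, the 2019 cohort and the refusers. On outcome it says: "Effectiveness will be calculated by comparing QOL in the intervention group versus the participation refusals".

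**Clinical endpoint.** Table 3 defines the combined endpoint as "Unplanned CV readmission and all-cause mortality". Clinical impact is a secondary objective.

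**The concern.** The two groups are compared on QOL and cost, yet the information that shows why a patient has no QOL form or no further bills is planned for one group only. A death in an app patient is an entry in the month-6 record. A death in a refuser leaves an online form that never arrives and bills that stop. The same pattern is left by a refuser who is well, has no further admissions and does not answer.

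Patients enter around a hospitalisation for decompensated heart failure with an ejection fraction of 40% or below, so some deaths within 6 months must be expected. Cost-effectiveness is a stated objective, and its effectiveness side rests on this comparison. A statistical analysis plan can set how deaths enter a utility or a cost. It cannot recover vital status that was never collected and for which no record access was sought.

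**Working it through.** **1. Planned data, side by side**

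| Item | App group | Refusers |
|---|---|---|
| QOL | Baseline and month 6 (Table 2); re-evaluation at month 12 | Online, months 6 and 12 |
| Costs | Yes | Yes, in selected patients |
| Death | Table 2, month 6 | Not listed |
| Hospitalisation, length of stay | Table 2, month 6 | Not listed; partly visible in bills |
| Emergency visit | Table 2, month 6 | Not listed; partly visible in bills |

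**2. Number of deaths that could go unseen**

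The protocol gives no mortality, so m (6-month mortality) is assumed. With n = 165 refusers (Sample size), expected deaths = n × m:
- m = 5%: 165 × 0.05 = 8.25, about 8
- m = 10%: 165 × 0.10 = 16.5, about 17
- m = 15%: 165 × 0.15 = 24.75, about 25

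Deaths in hospital at a participating centre may come to light through the bills. These counts are therefore upper figures for what is lost at each m.

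**3. Effect on the QOL contrast**

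Let u_A and u_R be mean utility in survivors, and m_A and m_R mortality, in the app and refusal groups.
- Survivors only in both groups: contrast = u_A − u_R.
- Death scored 0 in both groups: contrast = u_A(1 − m_A) − u_R(1 − m_R).

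The second cannot be computed without m_R. The two differ by u_R·m_R − u_A·m_A. This is zero when the two products are equal and can take either sign, and no term in it is given in the documents. The effect on the contrast therefore has neither a derivable size nor a derivable direction.

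**4. Effect on costs**

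Set the 6-month cost of a survivor to 1, with even accrual and death at mid-period. All values are illustrative.
- Death without a terminal admission: 0.5
- With a terminal admission costing 0.5, 1 or 2: 0.5 + 0.5 = 1.0, 0.5 + 1 = 1.5, 0.5 + 2 = 2.5

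A refuser who dies can be cheaper or dearer than one who survives.

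**5. What registering events would give**

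With 165 per group and an assumed event risk p in both, the 95% half-width of the risk difference is 1.96 × √(2p(1 − p)/165). This is 9.3 percentage points at p = 0.25 and 10.6 at p = 0.40. It covers sampling error only, not self-selection, and assumes that all 165 refusers allow access.

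**The case against.** **Bills already capture events.** Hospital costs come from billing departments, scheduled and unscheduled admissions are separated, and rehospitalisation at 30 and 90 days is to be assessed. None of this is restricted to app patients. This stands in part: some refuser readmissions and emergency visits at participating centres would be visible. The remaining gap is mainly deaths, especially outside hospital, and refusers whose costs are not collected because only selected ones are included. That events are registered for app patients alone is inferred from the scope of Table 2 and the listed refuser data. No sentence says so outright.

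**Both groups may be survivor means.** App-group QOL is also a questionnaire score, and a patient who has died has no month-6 value. This is right. A reader might infer that refuser utility is inflated relative to the app group by u × m, for example 0.65 × 0.10 = 0.065. That follows only if app deaths are scored 0 and refuser deaths left out, a rule the protocol does not state.

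**Costs.** A reader might infer that unseen deaths make refusers look cheap, or that lost follow-up time shrinks the cost denominator. Neither is supported. Step 4 of the working shows the direction is open, and the protocol averages cost per patient, not per unit of time. Bills also stop at death in the app group.

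**The comparator limitation is disclosed.** The Discussion concedes that the design has no distinct comparator and turns to a historical cohort, and the primary analyses are within-patient. So the lack of a concurrent contrast for the clinical endpoint is not hidden. But the disclosure sits uneasily with the control-group label under Sample size, and it does not address deaths mixed with non-response.

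**Confounding.** Refusers select themselves and no baseline clinical data are described for them. This stands, and limits any event comparison to description.

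**Conclusion.** The point holds as a gap in data collection. The protocol gives refusers a comparator role for QOL and cost but plans no record of their vital status or clinical events. The QOL comparison then rests on responding survivors, with deaths known in one group only, and refuser costs are truncated by unseen deaths in an unknown direction.

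The bias cannot be sized from the documents. The only figure offered is the assumed 8 to 25 deaths among 165 refusers at 5% to 15% mortality. This is a cheap improvement that should be made at protocol level, since later analysis cannot supply the missing data. It does not show that the planned comparison favours or disfavours the app.

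**What to change.** 1. For refusers who consent to record access, have the site record vital status with date of death, unplanned cardiovascular readmissions and emergency visits, with dates and length of stay, over the same 6 months as in Table 2. The source is hospital records and the bills already needed for their costs.
2. State that deaths are handled in the same way in both groups in the QOL or utility comparison and in the cost comparison, and are not counted as non-response.
3. Report the combined endpoint in refusers descriptively beside the app group, labelled non-randomised and subject to self-selection.

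**Cost.** Some site time for a record check at month 6, one added line of consent or information for refusers with ethics notification, and some refusers who decline access. No added visit or procedure is needed. The number of refusers who allow access should be reported, as it limits how complete the event data can be.
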